4.2 METHOD OF TREATMENT ASSIGNMENT AND MASKING

4.2.1 Treatment Assignment

This is a non-randomized study. After initial written informed consent has been obtained and eligibility has been established for a patient, the *site will obtain the patient's treatment assignment from* an interactive web-based response system (IWRS). Patients will retain the same patient number that was assigned in the parent study.

Patients will receive either 20 mg of FHTR2163 or 10 mg of FHTR2163 by ITV injection in the same study eye selected for injections in the parent study and at a dosing frequency that is consistent with the patient's original dosing schedule in the parent study (i.e., Q4W or Q8W).

FHTR2163—Genentech, Inc. 28/Protocol GR42558, Version 4

4.2.2 Masking Throughout the Study

The best corrected visual acuity (BCVA) examiner will be masked to study eye assignment *throughout the study*. The BCVA examiner will be permitted to perform only the refraction and the following study assessments: BCVA, low-luminance BCVA, and pretreatment intraocular pressure (IOP). The BCVA examiner will also be masked to the BCVA scores from the patient's previous visits and will only have access to a patient's refraction data from previous visits. Other site study staff will not be masked to study eye assignment *or patient treatment assignment*.

4.2.3 Masking During the Masked Period of the Study

The study will be masked until database lock of the parent study. After the masked period, the study will follow an open-label design.

The central reading center review team, consisting of graders and ophthalmologists experienced in the conduct of clinical trials, will be masked to patient treatment assignment during the masked period of the study. The central reading center will conduct masked independent review of CFP, FAF, NI, SD-OCT, and OCT-A images to provide an objective assessment of image evaluations. Contract research organization personnel, including clinical research associates, will not be masked to patient treatment assignment.

Patients will be masked to their treatment assignment (10 mg of FHTR2163 or 20 mg of FHTR2163). Sponsor personnel (except for IMC members) will be masked to treatment assignment until after database lock of the parent study, unless there is a need to unmask as determined by the IMC. Personnel responsible for PK/PD sample management, assays, and analysis may be unmasked as needed (i.e., to evaluate PK relationship to an adverse event).

For regulatory reporting purposes and if required by local health authorities, the Sponsor will break the treatment code for all serious, unexpected suspected adverse reactions that are considered by the investigator or Sponsor to be related to study drug.

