- Given that the changes in the study design could potentially unmask the parent study, an Internal Monitoring Committee has been added to monitor safety and study conduct during the masked period of the current study, which extends until database lock of the parent study (Sections 3.2, 4.2.2, and 5.1).
- Additional aqueous humor sample collections have been added at Week 24 and Week 72 to assess if sufficient HtrA1 target inhibition is achieved at the 10 mg of FHTR2163 dose level, and additional serum pharmacokinetic (PK) and anti-drug antibody samples have been added at Week 24 and Week 72 to enable assessment of immunogenicity at the 10 mg of FHTR2163 dose level. These sample collections have been added for all treatment arms to maintain masking (Appendix 1 and Appendix 2).

Other changes made to the protocol are as follows:

 Language around pre-injection prophylactic paracentesis procedures being performed outside of pre-specified aqueous humor collection visits has been added to the exclusion criteria, prohibited therapy criteria, and treatment interruption criteria. Specifically, given that such pre-injection prophylactic paracentesis procedures are not pre-specified procedures in the Informed Consent Form and procedure sequelae could confound the interpretation of the study outcomes, pre-injection prophylactic paracentesis procedures have been added as an exclusionary criterion and as a prohibited therapy. Treatment interruption criteria have been amended to indicate that if an enrolled patient is deemed to require a prophylactic paracentesis prior to study treatment administration, study treatment must be interrupted and may be resumed as determined by the investigator with consultation from the Medical Monitor. In addition, permitted therapy criteria have been clarified to allow for post-injection paracentesis as per clinical judgment. Furthermore, treatment interruption criteria have been amended to indicate that if an enrolled patient has had three consecutive post-injection paracentesis procedures performed in the study eye for treatment of adverse events, study drug must be interrupted. Study treatment may be resumed as determined by the investigator with consultation from the Medical Monitor (Sections 4.1.2, 4.4.1, 4.4.2, and 5.1.5; Table 1).

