9.4 ADMINISTRATIVE STRUCTURE

This trial will be sponsored and managed by Genentech, Inc. The Sponsor will maintain the medical, safety, data management, statistical programming, statistical analysis, and oversight of selected vendors during the study. A contract research organization (CRO) will manage the study, site monitoring, and selected vendors. Genentech will oversee the CRO.

An IWRS will be used for patient enrollment and management of study drug requests and shipments.

A central laboratory will be used for most laboratory assessments and for storage of other laboratory samples prior to being shipped to Sponsor or its designee for analysis. Data will be recorded on eCRFs through use of an EDC system or will be forwarded to the Sponsor electronically (e.g., safety lab data). A central reading center will conduct independent analyses of ocular images (e.g., FAF, NI, CFP, OCT-A, and SD-OCT) as needed.

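### Reading-center graders are masked to treatment only until parent-study database lock, with nothing in the protocol requiring masked reads of OLE images after that

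*Combined protocol and SAP*

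**What the plan says.** Section 4.2.3 sets the time limit: "The study will be masked until database lock of the parent study". After that the study is open-label. Within the section, the reading-center team "will be masked to patient treatment assignment during the masked period of the study". The next sentence reads "The central reading center will conduct masked independent review of CFP, FAF, NI, SD-OCT, and OCT-A images", and its purpose is "to provide an objective assessment of image evaluations". That sentence carries no end date of its own.

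Section 4.2.2 deals with masking that lasts the whole study and names one person: "The best corrected visual acuity (BCVA) examiner will be masked to study eye assignment". It does not list the reading center. Section 9.4 returns to the reading center's role with "A central reading center will conduct independent analyses of ocular images" and does not mention masking. Sections 2.4 and 6.7, the imaging footnotes in Appendices 1 and 2, and the imaging appendices (7 to 12) add no grader masking.

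The outputs that depend on these readings are change in GA area from both the parent-study and OLE baselines (2.4, 6.7) and the ocular imaging summaries among the safety analyses (6.4).

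**The concern.** A grader does not need the treatment assignment to outline a lesion. The purpose given for masked review is objectivity, and that purpose does not lapse when another study's database locks. The documents give no reason for graders to learn assignments later.

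Followed as written, one patient's GA-area series could contain early images read masked and later images read unmasked. A change in slope across lock could then partly reflect a change in reading conditions. The effect could also differ by dose. Section 3.1 assigns 10 mg to former sham patients who enrol once Version 4 is in force. They enter late, so more of their images tend to fall after lock than those of patients who entered earlier.

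**Working it through.** **Text check.** Three points bear on how long graders are masked.

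1. The time-limited sentence in 4.2.3 is explicit about its end, and the open-label statement in the same section confirms it.
2. The undated sentence on masked review follows it directly, under a heading confined to the masked period. It can be read as covering all OLE images, but its placement argues against that. At best the section is ambiguous.
3. The protocol separates study-long masking (4.2.2) from time-limited masking (4.2.3) and puts the reading center in the second group.

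No passage sends assignments to graders, so unmasked reading is permitted but not planned.

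**How many images are exposed.** The plan gives no figure to reproduce, no lock date and no accrual period. Inputs from the documents:

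- Version 1 is dated 15 July 2020 and Version 4 approval is stamped 22 September 2021. The gap is 434 days, and 434 / 7 = 62.0 weeks.
- FAF after Day 1 is scheduled at Weeks 24, 48, 72, 96, 120 and 144 in both Appendix 1 (Q4W) and Appendix 2 (Q8W).

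Nobody could be past OLE Week 62 at Version 4 approval, so at least 4 of the 6 FAF visits per patient (Weeks 72, 96, 120, 144) were still ahead. That describes the position at approval, not at lock.

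For the position at lock, assumptions are needed. Let A be the weeks from first to last Day 1 and L the weeks from last Day 1 to parent lock. On a patient's own clock, lock falls at week L + U, with U uniform on 0 to A. Then

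share after lock = (1/6) × Σ P(L + U < w), summed over w = 24, 48, 72, 96, 120, 144.

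The lower value A = 26 is inferred: 5.1.1.1 describes the study as ongoing on 26 March 2021, which is 180 / 7 = 25.7 weeks before Version 4 approval, and 3.1 expects further enrolment. A = 62 is the gap between the two document dates, not an enrolment period. A = 104 and L = 4 to 39 are assumptions.

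Example, A = 26 and L = 4: lock is uniform on Weeks 4 to 30. Week 24 falls after lock with probability 20/26 = 0.769, and the other five visits always do. The share is 5.769 / 6 = 96.2%.

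Example, A = 104 and L = 39: lock is uniform on Weeks 39 to 143. The probabilities are 0, 9/104, 33/104, 57/104, 81/104 and 1, which sum to 2.731. The share is 2.731 / 6 = 45.5%.

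| A (weeks) | L = 4 | L = 12 | L = 26 | L = 39 | L at which share is 50% |
|---|---|---|---|---|---|
| 26 | 96.2% | 91.0% | 80.8% | 72.4% | about 71 |
| 62 | 83.9% | 79.0% | 68.3% | 59.9% | about 53 |
| 104 | 69.2% | 64.1% | 53.8% | 45.5% | about 32 |

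With a constant discontinuation hazard leaving 50% at Week 144, each visit is weighted by 0.5^(w/144):

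| A (weeks) | L = 4 | L = 12 | L = 26 | L = 39 | L at which share is 50% |
|---|---|---|---|---|---|
| 26 | 95.0% | 88.3% | 75.2% | 65.5% | about 59 |
| 62 | 79.6% | 73.7% | 61.2% | 52.2% | about 42 |
| 104 | 63.4% | 57.7% | 46.8% | 38.6% | about 22 |

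**Whether the schedule itself would unmask graders.** FAF, OCT-A and near-infrared images fall at the same 6 visits in both appendices, color photographs at the same 3 (Weeks 48, 96, 144), and SD-OCT at the same 18 visits after Day 1 (every 8 weeks from Week 8 to Week 144). Planned image dates alone therefore do not reveal dosing frequency.

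**The case against.** The best textual objection is that the sentence on masked review has no end date, while its neighbors do ("Sponsor personnel (except for IMC members) will be masked to treatment assignment until after database lock of the parent study", for instance). It could be meant for every OLE image, in which case the fault is unclear drafting. That reading cannot be excluded, but the heading and the open-label statement weigh against it.

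A second objection is that ending the masking at parent lock is deliberate, to protect the parent study. The amendment rationale says "an Internal Monitoring Committee has been added to monitor safety and study conduct during the masked period of the current study", in response to the risk of unmasking the parent study. That supports the inference, but the stated response to that risk is the committee. Neither that rationale nor the open-label label explains why graders should learn assignments.

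The objections on consequence largely stand. GA area is exploratory, 6.7 is descriptive, and its one named contrast is HTRA1 carrier status rather than treatment arm. Imaging adverse events are classified by investigators (5.3.5.3), and site staff other than the visual acuity examiner are unmasked anyway (4.2.2). Dose is tied to parent arm and entry time, and masking would not remove that confounding. The shares above rest on assumed accrual and lag.

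It is also fair that the protocol describes the masked assignment as 10 mg or 20 mg, so naming frequency and parent arm goes further. That is justified: the arms are defined by dose and interval, and former sham status reveals the 10 mg dose for anyone enrolling under Version 4.

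**Conclusion.** The point holds as an optional improvement. The protocol limits grader masking to the period before parent-study lock, and no passage in the documents extends it. The risk is differential reading in exploratory and descriptive outputs; the primary adverse event endpoints are hardly touched.

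Under the stated assumptions, 46% to 96% of scheduled FAF images would be taken after lock, or 39% to 95% with 50% discontinuation by Week 144. A majority is not established: without dropout the share falls below half if lock comes more than about 53 weeks after the last Day 1 (62-week accrual) or 32 weeks (104-week accrual). None of these figures measures bias or counts images actually read unmasked. The conclusion also depends on the Central Reading Center Manual, which was not available, not already containing the rule.

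**What to change.** Add one sentence to 4.2.2 or 4.2.3: reading-center graders remain masked to dose, dosing frequency and parent-study arm for all OLE images until OLE database lock, and assignments are not sent to the reading center. Align the Central Reading Center Manual if it does not already say so.

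The cost is that sentence and, if needed, a line in the manual, carried in the next amendment with IRB/EC approval under 9.6. No visit, image or sample changes. One limit remains: a missed image is retaken at the next scheduled visit, so a make-up image at an off-schedule week could reveal Q4W dosing to a grader who sees the visit date.

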4.3 STUDY TREATMENT AND OTHER TREATMENTS RELEVANT TO THE STUDY DESIGN

The investigational medicinal product (IMP) for this study is FHTR2163.

4.3.1 Study Treatment Formulation and Packaging

FHTR2163 will be supplied by the Sponsor. Information on the formulation and packaging are provided in the pharmacy manual.

4.3.2 Study Treatment Dosage, Administration, and Compliance

Patients will receive 20 mg of FHTR2163 *or* 10 mg of FHTR2163 by ITV injection in the study eye at a dosing frequency that is consistent with the patient's original dosing schedule in the parent study (i.e., Q4W or Q8W).

FHTR2163—Genentech, Inc. 29/Protocol GR42558, Version 4

Upon implementation of protocol Version 4, all eligible patients in the sham control arms of the parent study that are newly enrolling in the OLE study will receive 10 mg of FHTR2163 (Q4W or Q8W; see Figure 1). Patients currently enrolled in the OLE study (i.e. enrolled prior to implementation of protocol Version 4) will continue receiving their current dosing regimen for the remainder of the study.

Refer to the pharmacy manual for detailed instructions on drug preparation and administration.

Details on treatment administration (e.g., *frequency of* dose and timing) should be noted on the Study Drug Administration electronic Case Report Form (eCRF). Cases of accidental overdose or medication error, along with any associated adverse events, should be reported as described in Section 5.3.5.14.

Patients will be monitored before and after injections as outlined in Section 5.1.4. Guidelines for treatment interruption or discontinuation for patients who experience adverse events are provided in Section 5.1.5.

4.3.3 Investigational Medicinal Product Handling and Accountability

All IMPs required for completion of this study will be provided by the Sponsor. The study site (i.e., investigator or other authorized personnel [e.g., pharmacist]) is responsible for maintaining records of IMP delivery to the site, IMP inventory at the site, IMP use by each patient, and disposition or return of unused IMP, thus enabling reconciliation of all IMP received, and for ensuring that patients are provided with doses specified by the protocol.

The study site should follow all instructions included with each shipment of IMP. The study site will acknowledge receipt of IMPs supplied by the Sponsor per agreed method (i.e., returning the appropriate documentation form or updating IWRS) to confirm the shipment condition and content. Any damaged shipments will be replaced. The investigator or designee must confirm that appropriate temperature conditions have been maintained during transit, either by time monitoring (shipment arrival date and time) or temperature monitoring, for all IMPs received and that any discrepancies have been reported and resolved before use of the IMPs. All IMPs must be stored in a secure, environmentally controlled, and monitored (manual or automated) area in accordance with the labeled storage conditions, with access limited to the investigator and authorized staff.

Only patients enrolled in the study may receive IMPs, and only authorized staff may supply or administer IMPs.

IMPs will either be disposed of at the study site according to the study site's institutional standard operating procedure or be returned to the Sponsor with the appropriate documentation. The site's method of destroying Sponsor-supplied IMPs must be agreed

to by the Sponsor. The site must obtain written authorization from the Sponsor before any Sponsor-supplied IMP is destroyed, and IMP destruction must be documented on the appropriate form.

Accurate records of all IMPs received at, dispensed from, returned to, and disposed of by the study site should be recorded on the drug accountability log.

Refer to the pharmacy manual and/or the FHTR2163 Investigator's Brochure for information on IMP handling, including preparation and storage, and accountability.

4.3.4 Continued Access to FHTR2163

Currently, the Sponsor (Genentech, a member of the Roche Group) does not have any plans to provide Genentech IMP (FHTR2163) or any other study treatments to patients who have completed the study. The Sponsor may evaluate whether to continue providing FHTR2163 in accordance with the Roche Global Policy on Continued Access to Investigational Medicinal Product, available at the following website:

http://www.roche.com/policy_continued_access_to_investigational_medicines.pdf

4.4 CONCOMITANT THERAPY

Concomitant therapy consists of any medication (e.g., prescription drugs, over-thecounter drugs) other than protocol-specified procedural medications (e.g., dilating drops, proparacaine) used by a patient in addition to protocol-mandated treatment through the final visit. All such medications should be reported to the investigator and recorded on the Concomitant Medications eCRF.

4.4.1 Permitted Therapy

In general, investigators may manage patients' preexisting conditions or new-onset conditions as clinically indicated and per local standard practice, with the exception of prohibited therapies defined in Section 4.4.2. Of note, the following are some common therapies that are permitted:

- Treatments as clinically indicated for onset of ocular hypertension or glaucoma are permitted in either eye during study participation
- Treatments as clinically indicated for onset of cataract or posterior capsular opacification are permitted in either eye during study participation

Treatment interruption criteria may apply with cataract surgery (see Section 5.1.5).

- Corticosteroids (ITV, subtenon, topical, device implant, oral, or IV)
- Patients who use hormone-replacement therapy or other maintenance therapy should continue their use

• Anti-VEGF treatment in the non-study eye is permitted

Intravitreal administration of FDA-approved anti-VEGF agents is permitted at the discretion of the evaluating investigator if a patient's non-study eye requires treatment for nAMD. Treatment in the non-study eye may be administered at the same visit as the study eye treatment; however, all study assessments and study eye treatment per protocol should be completed prior to anti-VEGF administration in the non-study eye. Individual trays and sterile preparation must be separately prepared for each eye treatment.

• Paracentesis in the study eye after study drug administration is permitted per clinical judgment for treatment of adverse events

For patients with a history of repeated paracentesis after study drug administration, refer to treatment interruption criteria (see Table 1).

4.4.2 Prohibited Therapy

The following medications and therapies are prohibited during the study, and patients who receive any of the following therapies may have study treatment interrupted or discontinued and/or may be discontinued from the study (see Section 5.1.5):

- Systemic anti-VEGF agents
- ITV anti-VEGF agents in the study eye
- Concurrent non-study eye treatment with unapproved anti-VEGF therapy for nAMD
- Systemic or IV immunomodulatory therapy (e.g., azathioprine, methotrexate, mycophenolate mofetil, cyclosporine, cyclophosphamide, anti-tumor necrosis factor agents, eculizumab, tocilizumab)
- Treatment with photodynamic therapy in either eye
- Other experimental therapies, including, but not limited to, stem-cell treatments, gene therapy, and long-acting delivery platforms or formulations
- Prophylactic paracentesis in the study eye prior to study treatment administration (not including anterior chamber paracentesis to enable collection of aqueous humor samples)

For patients that require prophylactic paracentesis prior to study drug administration, refer to treatment interruption criteria (see Table 1).

4.5 STUDY ASSESSMENTS

Schedules of activities to be performed during the study are provided in Appendix 1 and Appendix 2. All activities should be performed and documented for each patient.

4.5.1 Informed Consent Forms

Written informed consent for participation in the study must be obtained before performing any study-related procedures. Informed Consent Forms for enrolled patients and for patients who are not subsequently enrolled will be maintained at the study site.

Week 76 evaluations in the parent study must be completed and reviewed to confirm that patients meet all eligibility criteria prior to enrollment at the Day 1 visit in this extension study. The investigator will maintain a log to record details of all patients who sign the Informed Consent Form to document each patient's eligibility or ineligibility to be enrolled in the study, as applicable.

4.5.2 Physical Examinations

A targeted physical examination should include an evaluation of the head, eyes, ears, nose, throat, and cranial nerves. The patient's weight will be measured as well. Any abnormality identified at Day 1 (screening) should be recorded on the General Medical History and Baseline Conditions eCRF. If any abnormalities are noted during the study, the patient may be referred to their primary care physician or an appropriate specialist for further evaluation. Changes from baseline abnormalities should be recorded in patient notes. New or worsened clinically significant abnormalities should be recorded as adverse events on the Adverse Event eCRF.

4.5.3 Vital Signs

Vital signs will include measurements of respiratory rate, pulse rate, and systolic and diastolic blood pressure while the patient is in a seated position after resting for 5 minutes, and temperature.

4.5.4 Ocular Assessments

Ocular assessments will include the following, to be performed on both eyes (with the exception of post-injection safety assessments) at timepoints specified in the schedules of activities (see Appendix 1 and Appendix 2). A detailed examination to evaluate for signs of intraocular inflammation (IOI) should be performed prior to any study drug administration.

• BCVA assessment as determined by Early Treatment Diabetic Retinopathy Study (ETDRS) chart at a starting distance of 4 m

Perform assessment prior to dilating eyes. Refer to Appendix 3 and the Clinical Edge Visual Acuity Certification Procedure Manual for more information on BCVA assessments.

• Low-luminance BCVA assessment as determined by ETDRS chart at a starting distance of 4 m under low-luminance conditions

Perform assessment prior to dilating eyes. Refer to Appendix 4 and the Clinical Edge Visual Acuity Certification Procedure Manual for more information on low-luminance BCVA assessments.

• Pre-injection IOP measurement

Perform assessment prior to dilating eyes. The method of IOP measurement used for a patient must remain consistent throughout the study.

• Slit-lamp examination

Perform examination prior to dilating eyes. Refer to Appendix 5 for grading scales for anterior chamber flare or cells and vitreous cells.

- Dilated binocular indirect high-magnification ophthalmoscopy examination
- Finger-counting test, followed by hand motion and light perception tests when necessary, performed for the study eye within 15 minutes after study drug injection (see Appendix 6)
- Post-injection IOP measurement in the study eye between 30 and 50 minutes after injection on study treatment visit days

If there are no safety concerns, the patient will be discharged from the clinic. If the IOP is increased by \geq 10 mmHg compared with the pre-injection measurement or is of concern to the investigator, the IOP will be measured again at 60–80 minutes after injection. If the IOP value remains a concern to the investigator, the patient will remain in the clinic and will be treated as necessary in accordance with the investigator's clinical judgment prior to the patient's discharge (see Section 5.3.5.2 for guidance on recording adverse events of increased IOP).

The method of IOP measurement used for a patient must remain consistent throughout the study.

